Study design	This is a interventional, multicenter, non-randomized, parallel-group, opened designed study lasting during 12 months for approximately 130 patients with type 2 diabetes and obesity.
Population	The study is expected to include approximately 100 patients with T2DM and obesity who will be on active management and another 30 patients whose case records will be collected from routine clinical practice for comparison purposes.
Inclusion criteria	
 • Signed Informed Consent. Written informed consent must be obtained before any assessment is

	
performed.
 
 • ≥ 18 years • Type 2 diabetes • The Body Mass Index is from 28 to 40 kg/m²
Exclusion criteria	
 • Pregnant or nursing (lactating) women, where pregnancy is defined as the state of a female after conception and until the termination of gestation. • Type 1 diabetes • Proliferative retinopathy • Renal impairment: serum creatinine >1.5 mg/dL, creatinine clearance < 40 ml/min and/or proteinuria • The lack of ability to perform the physical exercises due to the orthopedic or cardiovascular disorders • Chronic alcoholism, acute alcoholic intoxication
Investigational and reference therapy	
No drugs will be supplied during the study. Hypoglycemic drug therapy will be provided according routine standard practice without any special changes.

Efficacy assessments	
 • Weight reduction • Control of glycemic in HbA1C and FPG • Blood pressure • Lipid profile indicators
Safety assessments	
 • Adverse events • Vital signs • Laboratory assessments • ECG
Other assessments	
 • HE supply form • Survey for hypoglycemic assessment • Scale of individual perception of physical exercises (Borg scale)
Data analysis	
Descriptive statistics will be applied in the study to describe the sample size of the patients at baseline and at follow-up visits, demographic data recorded during the examination of the study parameters, as well as their changes.
 
The primary analysis of the proportion of the patients with response on the treatment will be performed using multivariate logistic regression and calculating odds ratios with corresponding 95% CI. To control the potential confounding factors, age, sex, BMI, disease duration, the baseline values of HbA1c will be taken into account in the regression model.

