10.5.2 Hypoglycemia Perspectives Questionnaire

The impact of T2DM on various aspects of patient's health-related quality of life will be assessed by the following validated instruments, each of which will be performed as indicated in Table 7-1 and Table 7-2.

- Health Questionnaire EQ-5D-3L
- Hypoglycemia Perspectives Questionnaire
- DTSQ

Doctor (investigator or acting as investigator) should fill out this survey based on what the patient says. The survey will be filled out in Russian before the patient attends the 1st visit of the study. The doctor should ask the patient to answer the questions and fill out the survey. The originals should be kept with other primary documents in the research center.

The patient should fill out the Diary of self-control in between the visits. The diary has teared-off pages where all data on food intake, the level of glucose before and 2 hours after the food intake and hypoglycemia therapy should be mentioned. Additionally, the patient should register in the Diary the change in glucose level, BP and pulse before and after physical exercises. Completed pages should be given to the doctor by the patient at each visit. In case of AEs or SAEs they should be registered according to the instructions of the Chapter 11. Reporting system is also described in Chapter 11.

11 Safety monitoring

Any serious adverse events will be reported to the Local Ethics Committee within 24 hours of the occurrence. All serious adverse events will also be reported to Novartis Drug Safety & Epidemiology (DS&E) within 24 hours of the investigator (or designee) being aware of the serious adverse event. Specific definitions of adverse events, and serious adverse events, are outlined below, along with reporting criteria required by Novartis.

Adverse events (AE)

Information about all AEs, whether volunteered by the patient, discovered by investigator questioning, or detected through physical examination, laboratory test or other means, will be collected and recorded on an Adverse Event Case Report Form and will be followed up as appropriate.

An AE is any undesirable sign, symptom or medical condition occurring after starting study treatment, even if the event is not considered to be part of lifestyle changes implied by this study.

Medical conditions/diseases present before starting study treatment will only be considered adverse events if they worsen after starting study treatment (any procedures specified in the

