protocol). Adverse events (but not serious adverse events) occurring before starting study treatment but after signing the informed consent form will be recorded on the Medical History/Current Medical Conditions Case Report Form. Abnormal laboratory values or test results constitute adverse events only if they induce clinical signs or symptoms, are considered clinically significant or require therapy, and are recorded on the Adverse Events Case Report Form under the signs, symptoms or diagnosis associated with them.

As far as possible, each adverse event will also be described by:

1. the severity grade (mild, moderate, severe)
2. its relationship to the drug(s) of interest (suspected/not suspected)
3. its duration (start and end dates or if continuing at final exam)
4. whether it constitutes a serious adverse event (SAE)

Serious Adverse Events (SAEs)

Information about all serious adverse events will be collected and recorded on the Serious Adverse Event Report Form. To ensure patient safety each serious adverse event will also be reported to Novartis DS&E within 24 hours of the investigator learning of its occurrence.

An SAE is defined as an event which:

- Is fatal or life-threatening
- Results in persistent or significant disability/incapacity
- Constitutes a congenital anomaly/birth defect
- Requires inpatient hospitalization or prolongation of existing hospitalization, unless hospitalization is for:
 - Routine treatment or monitoring of the studied indication, not associated with any deterioration in condition (specify what this includes)
 - Elective or pre-planned treatment for a pre-existing condition that is unrelated to the indication under study and has not worsened since the start of the drug of interest
 - Social reasons and respite care in the absence of any deterioration in the patient's general condition
- Is medically significant, i.e., defined as an event that jeopardizes the patient or may require medical or surgical intervention to prevent one of the outcomes listed above e.g. may require treatment on an emergency outpatient basis for an event not fulfilling any of the definitions of a SAE given above and not resulting in hospital admission
- Transmission of infectious agent via medicinal product

No specific SAEs exempt from this reporting process are planned in this protocol.

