Any SAE occurring after the patient has provided informed consent and until 4 weeks after the patient has stopped study participation will be reported. Serious adverse events occurring more than 4 weeks after study discontinuation will be reported to Novartis DS&E only if a relationship with any Novartis study therapy is suspected by the investigator.

Local Department of Pharmacovigilance (Clinical Safety) of Novartis Pharma in Russia

Phone: [REDACTED]

Fax: [REDACTED]

Email: [REDACTED]

Specialists in drug safety: [REDACTED]

As far as possible, each SAE will also be described by (but not limited to):

- Its duration (onset date = date of 1st signs or symptoms, and end dates)
- The seriousness criteria and severity if applicable (mild, moderate, severe)
- Its relationship to current investigational regimen (suspected / not suspected as judged by the investigator)
- The action(s) taken and investigation results if applicable
- Concomitant medication details
- Outcome

Notification of serious adverse events to Novartis Pharmaceuticals Drug Safety & Epidemiology (DS&E)

Each Serious Adverse Event (SAE) will be reported by the investigator to Novartis DS&E within 24 hours of learning of its occurrence, even if it is not felt to be related to study procedures or Novartis treatment. Follow-up information about a previously reported SAE will also be reported to Novartis DS&E within 24 hours of receiving it. If the SAE has not been previously documented (new occurrence) and it is thought to be related to study treatment, Novartis Drug Safety Department may contact the investigator to obtain further information.

If warranted, an Investigator Notification may be issued, to inform all investigators involved in any study with the same drug that this serious adverse event has been reported.

Reporting procedures

The investigator will complete the SAE Report Form, assess the relationship to study treatment/study procedures and send the completed and signed form by fax within 24 hours to Novartis DS&E. The original and the duplicate copies of the SAE Form, and the fax confirmation sheet will be kept with the case report forms at the study site.

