12.2 Safety assessment

The safety variables will be analyzed in the Safety Populations, missing measurements will not be imputed.

Adverse events

Adverse events will be coded using the Medical Dictionary for Regulatory Activities (MedDRA, version 19).

Data on adverse events will be presented in terms of the number and proportion of patients with any adverse events overall, by system organ class (SOC) and preferred term (PT).

The number (proportion) of patients with AE and the number of AE will be tabulated by system organ class and preferred term, as well as by relationship to study treatment and severity. Within each system organ class and preferred term, each patient will be counted only once with the closest relationship to the study treatment or maximum severity. In the case of missing value of severity or relationship, the AE will be considered in the table as "severe" and "related", respectively.

The following tables will be provided:

- The number (proportion) of patients with AE and the number of AEs by system organ class and preferred term;
- The number (proportion) of patients with AE and the number of AEs related to study treatment by system organ class and preferred term;
- Number (proportion) of patients with AE and the number of AEs by severity, by system organ class and preferred term;
- The number (proportion) of patients with AE and the number of AEs that led to discontinuation of the program (for the active group), by system organ class and preferred term;
- The number (proportion) of patients with AE and the number of AEs that are fatal, by system organ class and preferred term;
- The number (proportion) of patients with SAE and the number of SAE, by system organ class and preferred term;

The analysis will not include AEs that started before the start of a lifestyle change program for patients in the active group. In the case of a partial start date for AE, it will be compared as far as possible with the program start date to determine if it occurred prior to the start of the program. If the available information is not sufficient, the AE will be considered to have started after the beginning of the program.

The analysis of the SAE will include all registered SAE. Data on all AE / SAE will be presented in the form of listings.

Laboratory data

Laboratory investigations were conducted on Visit 1, Week 12 and 48 and included the following parameters:

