Table 4.3.5 Analysis of changes in WHR compared to baseline values (FAS)

Table 4.4.1 Descriptive statistics for HbA1c values and their changes in percent and absolute units by study visits (FAS)

Table 4.4.2 Analysis of absolute changes of HbA1c compared to baseline values at 3, 6, 9 and 12 months of observation (FAS)

Table 4.4.3 Analysis of changes in HbA1c in % compared to baseline values at 3, 6, 9 and 12 months of observation (FAS)

Table 4.4.4. Reduction of HbA1c level by at least 0.5% of baseline by study visits (FAS)

Table 4.4.5 Analysis of the reduction in HbA1c level by at least 0.5% from baseline (FAS)

Table 4.4.6 Analysis of the achievement of HbA1c \leq 7% at 12 months of observation (FAS)

Table 4.4.7 Descriptive statistics for FBG values and their changes in percent and absolute units by study visits (FAS)

Table 4.4.8 Analysis of the absolute changes in FBG compared to the baseline values at 3, 6, 9 and 12 months of observation (FAS)

Table 4.4.9 Analysis of FBG changes in % compared to baseline values at 3, 6, 9 and 12 months of observation (FAS)

Table 4.5.1 - 4.5.2 Descriptive statistics for values of SBP and DBP and their changes in absolute units by study visits (FAS)

Table 4.5.3 - 4.5.4 Analysis of absolute changes in SBP and DBP compared to baseline values at 3, 6, 9 and 12 months of observation (FAS)

Table 4.5.6 - 4.5.8 Decrease in SBP and DBP by at least 5 mmHg from baseline (FAS)

Table 4.5.9 - 4.5.10 Analysis of the decrease in SBP and DBP by at least 5 mmHg from baseline by study visits (FAS)

Table 4.6.1 - 4.6.4 Descriptive statistics for lipid profile values (cholesterol, triglycerides, LDL, HDL) and their changes in percent and absolute units for study visits (FAS)

Table 4.7.1 - 4.7.4 Analysis of changes in % of lipid profile (cholesterol, triglycerides, LDL, HDL) compared to baseline values at 3 and 12 months of observation (FAS)

Table 4.8.1 - 4.8.4 Analysis of absolute changes in lipid profile (cholesterol, triglycerides, LDL, HDL) compared to baseline values at 3 and 12 months of observation (FAS)

Table 5.1.1 Frequency table for adverse events (Safety Population)

Table 5.1.2 Frequency table for adverse events by severity (Safety Population)

Table 5.1.3 Frequency table for adverse events by relationship to study treatment (Safety Population)

Table 5.1.4 Frequency table for adverse events leading to discontinuation (Safety Population)

Table 5.1.5 Frequency table for fatal adverse events (Safety Population)

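### Non-serious AEs are rated against an undefined drug but tabulated as related to study treatment, and a missing rating counts as related even for controls

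*Protocol*

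**What the plan says.** The Protocol synopsis classes the investigation as non-drug and states "No drugs will be supplied during the study". Background antidiabetic therapy continues as in routine practice in both groups.

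Protocol section 11 opens its list of AE descriptors with "As far as possible, each adverse event will also be described by". The second item is "its relationship to the drug(s) of interest (suspected/not suspected". The drugs in question are not defined anywhere.

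For SAEs, the descriptor list in the same section asks for "Its relationship to current investigational regimen (suspected / not suspected as judged by the investigator". Its reporting procedure asks the investigator to assess the relationship to the treatment or procedures of the study.

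The AE definition does explain what study treatment means. Pre-existing conditions will "only be considered adverse events if they worsen after starting study treatment (any procedures specified in the", with the parenthesis closing on the word protocol.

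SAP 12.2 plans tables of AEs related to study treatment and of AEs by relationship. SAP 18.1 lists the latter, Table 5.1.3, as "Frequency table for adverse events by relationship to study treatment", for the Safety Population. SAP 12.2 does not define study treatment. Its rule for gaps is "In the case of missing value of severity or relationship, the AE will be considered in the table as" severe and related, respectively. SAP section 7 puts controls in the Safety Population once their observation has started.

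**The concern.** The item collected and the label on the table are about different things. A programme of diet, exercise and classes can cause harm. Protocol section 10 itself notes that physical activity can provoke hypoglycaemia in patients on insulin or on agents that stimulate insulin secretion. If the investigator is asked only about a drug, the answer is not a judgement on the programme, yet the SAP reports it as though it were.

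The missing-value rule is a separate problem. It has no group limit, and controls do not attend the programme. A gap in a control's record becomes an event related to something that patient did not receive. With only 30 controls planned, a few such records would change how the table reads. The primary endpoint is not touched; what is at stake is whether one planned set of safety tables can be interpreted.

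**Working it through.** The plan states no figure on this point, so there is none to reproduce. The check is a comparison of wording, followed by a calculation of scale on assumed rates.

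**Step 1. What relationship is judged against, place by place.**

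| Place | Relationship to what |
|---|---|
| Protocol 11, AE descriptors, item 2 | undefined drugs of interest |
| Protocol 11, SAE descriptors | "Its relationship to current investigational regimen" |
| Protocol 11, SAE reporting procedure | treatment or procedures of the study |
| Protocol 11, AE definition (meaning of study treatment) | procedures laid down in the protocol |
| SAP 12.2 and Table 5.1.3 | study treatment, undefined in the SAP |

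If the SAP's term takes the Protocol's meaning, the table heading covers the programme, but the item collected for non-serious AEs does not. If it takes a drug meaning, the heading matches the item, but the table says nothing about the intervention. Under neither reading do the related-AE tables measure relationship to the programme for non-serious AEs.

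**Step 2. An example.** Take hypoglycaemia after exercise in a patient on insulin. Rated against a drug, it may be suspected because of the background insulin, or not suspected because the study has no drug of its own. An exercise injury, read literally, is not suspected. None of these answers concerns the programme.

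**Step 3. Reach of the missing-value rule.** SAP 12.2 limits the table of AEs leading to programme discontinuation to the active group, and its exclusion of pre-programme AEs is also written for active patients. The missing-as-related rule has no such limit, and Table 5.1.3 covers controls through the Safety Population. Within each system organ class and preferred term, a patient is counted once at the closest relationship, so one blank AE is enough to place that patient in the related row.

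**Step 4. Scale.** Planned group sizes are 100 active and 30 control (SAP section 6). The documents give no AE rate and no missing rate; those below are assumptions.

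- Weight of one patient: 1/100 = 1.0 point in the active group; 1/30 = 3.3 points in the control group.
- Patients moved to related, at most = n × AE rate × share missing. With AE rates of 30–70% and 5–20% missing:
  - Controls: 30 × 0.30 × 0.05 = 0.45 (about 0.5) to 30 × 0.70 × 0.20 = 4.2 patients.
  - Active: 100 × 0.30 × 0.05 = 1.5 to 100 × 0.70 × 0.20 = 14 patients.
- Table shown when 50% of each group have an AE, and the truth is 10% programme-related in the active group and 0% in controls:
  - 10% missing in both groups: active 10 + (50 − 10) × 0.10 = 14.0%; control 50 × 0.10 = 5.0%. The difference is 9.0 points against a true 10.
  - None missing in the active group, every control AE blank: 10% against 50 × 1.00 = 50%, a reversed comparison. This is an extreme case.
  - Nothing missing: no effect.

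**The case against.** The strongest reply is that this is loose terminology with limited reach, and much of that stands.

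- A reader might infer that all causality in this study is judged against a drug. It is not: SAEs are rated against the regimen and against study treatment or procedures. The drug wording governs the general AE descriptor list, so non-serious AEs are affected and SAEs are left with inconsistent terms.
- A reader might infer that the plan cannot describe the programme's safety at all. That goes too far. The all-AE, severity, SAE, fatal-AE and programme-discontinuation tables do not use the relationship field (severity has its own missing-value rule).
- A reader might infer that the field will usually be blank for controls. The documents do not show this. The item is binary, so a control AE can be rated not suspected. Controls also receive diabetes drugs and undergo protocol examinations, so the item is not empty for them on every reading. Protocol 12.2 and 12.3 provide automatic checks, completeness review and queries. Blanks are possible, because the descriptors are collected only as far as feasible, but their frequency cannot be predicted, and no single count of misclassified controls can be defended.
- Counting missing as related is a common conservative convention. In the active group it errs towards showing more harm. The objection is only to applying it to controls in a table meant to describe the programme.

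What the reply does not remove is the mismatch between the item collected and the table's label. The Protocol's own explanation of study treatment makes that mismatch plainer.

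**Conclusion.** The point holds in a limited form. As written, the related-AE tables do not measure relationship to the programme for non-serious AEs, and SAEs enter them under differently worded terms. This follows from the text and needs no assumption.

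The missing-as-related rule can also show control AEs as related to a programme controls did not receive. Its size depends entirely on how many values are missing and in which group: zero if none, 3.3 points for each affected control patient, and roughly 0.5 to 4.2 of 30 controls under the assumed rates. Those rates are illustrative and do not come from the documents.

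This is a minor correction that leaves efficacy and the other AE tables as they are.

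**What to change.** - In Protocol section 11, replace the second AE descriptor with relationship to the study programme or study procedures, in line with the Protocol's own explanation of study treatment. Use the same term for SAEs and define it in SAP 12.2.
- Limit the programme-related AE tables and the missing-as-related rule to the active group. List any procedure-related AE in controls separately so that it is not lost.
- Report the number of missing relationship values by group.

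The cost is a short wording change to the Protocol, CRF guidance and SAP. The Protocol change needs an amendment with ethics approval under section 16. The SAP changes need no new data. The SAP describes laboratory and ECG assessments in the past tense, so some AEs may already have been rated against a drug. Those need re-rating by the investigator or, failing that, a stated limitation in the report.

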12.1 Site monitoring

Before study initiation at a site initiation visit or at an investigator meeting, a Novartis representative will review the protocol and eCRF with the investigators and their staff. During the study, the field monitor will visit the site regularly to check the completeness of patient records, the accuracy of entries on the eCRF, the adherence to the protocol and to Good Clinical Practice (GCP), the progress of enrollment. Key study personnel must be available to assist the field monitor during these visits.

The investigator/qualified site staff must maintain source documents for each patient in the study, consisting of, but not limited to, case and visit notes (hospital or clinic medical records) containing demographic and medical information, laboratory data, ECGs, and the results of any other tests or assessments. All information on eCRF must be traceable to these source documents in the patient’s file. The investigator must also keep the original informed consent form signed by the patient (a dated and signed copy is given to the patient).

The investigator/qualified site staff must give the monitor access to all relevant source documents to confirm their consistency with eCRF entries. Novartis monitoring standards require full verification for the presence of informed consent, adherence to the inclusion/exclusion criteria, documentation of SAEs, and of data that will be used for all primary variables. Additional checks of the consistency of the source data with the eCRF are performed according to the study-specific monitoring plan. No information in source documents about the identity of the patients will be disclosed.

